10.1 Primary Efficacy Endpoints

- **Change from Baseline to Week 12 in Weekly DGSSS:** Baseline is the baseline value from the lead-in study RLM-MD-01 or RLM-MD-02 and Week 12 is the 12th week of the 40-week Treatment Period (Days 78 to 84).
- **Vomiting Week-12 Responder:** Vomiting Week-12 Responder is defined as a participant with zero weekly vomiting episodes during each of the last 6 weeks of the first 12 weeks of the 40-week Treatment Period.

A participant will be considered as Vomiting Week 12 non-Responder if the weekly number of vomiting episodes is missing from the diary for any of the last 6 weeks of the first 12 weeks of the 40-week Treatment Period.

10.2 Secondary Efficacy Endpoints

- **Nausea Week 12 responder:** Nausea responder defined as a participant who has a ≥ 2 -point improvement in the weekly symptom score at each of the last 6 weeks of the first 12 weeks of the 40-week Treatment Period
- **Abdominal pain Week 12 responder:** Abdominal pain responder defined as a participant who has a ≥ 2 -point improvement in the weekly symptom score at each of the last 6 weeks of the first 12 weeks of the 40-week Treatment Period
- **Bloating Week 12 responder:** Bloating responder defined as a participant who has a ≥ 2 -point improvement in the weekly symptom score at each of the last 6 weeks of the first 12 weeks of the 40-week Treatment Period

- Postprandial fullness Week 12 responder: Postprandial fullness responder defined as a participant who has a ≥ 2 -point improvement in the weekly symptom score at each of the last 6 weeks of the first 12 weeks of the 40-week Treatment Period
- Change from Baseline to Week 40 in Average Weekly DGSSS: Average weekly scores are derived as the average of the weekly scores from Week 37 to Week 40
- Change from Baseline to Week 46 in Average Weekly DGSSS: Average weekly scores are derived as the average of the weekly scores from the six weeks of the Randomized Withdraw Period
- Change from Baseline to Week 40 in Vomiting Frequency: Average weekly number of vomiting episodes are derived as the average of the weekly number of vomiting episodes from Week 37 to Week 40
- Change from Baseline to Week 46 in Vomiting Frequency: Average weekly number of vomiting episodes are derived as the average of the weekly number of vomiting episodes from the six weeks of the Randomized Withdraw Period
- Vomiting Week 40 Responder: Vomiting responder defined as a participant with zero weekly vomiting episodes during each of the last 4 weeks of the 40-week Treatment Period(Week 37 to Week 40)

11 Safety Analyses

The safety analysis for the double-blind Treatment Period will be performed using the Safety Population. For the RW Period, the safety analysis will be performed using the RW Population. The safety parameters will include adverse events (AEs), clinical laboratory, electrocardiogram, and vital sign parameters.

The Day 1 for the safety analyses in the double-blind treatment period is the date of the first double-blind study treatment in this study. Day 1 for the safety analyses in the RW period is the re-randomization date.

11.1 Adverse Events

Adverse events will be coded by system organ class and preferred term using the *Medical Dictionary for Regulatory Activities (MedDRA)*, version 23.0 or newer.

An AE will be considered a treatment-emergent adverse event (TEAE) for the study if it was present after the first dose of study intervention or was present before the date of the first dose of study intervention and increased in severity or became serious after the first dose of study treatment during the study. Per case report form instructions, a new AE record will be created with a new AE onset date for any AE that worsens. Therefore, TEAEs can simply be identified as those AEs with recorded onset date on or after the date of the first dose of study intervention and within 30 days of the last dose of study intervention in the study. An AE that occurs more than 30 day after the last dose of study drug in the study will not be counted as a TEAE for the study.

An AE will be considered a treatment-emergent SAE (TESAE) if it is a TEAE that also is an SAE.

All TEAEs related summary will be presented by treatment group for the Treatment Period and by treatment sequence for the RW Period separately. A TEAE will only be counted in the double-blind treatment period if it starts between the date of the first dose of study treatment (inclusive) in the double-blind treatment period and the date of the first dose of study treatment (exclusive) in the RW period or within 30 days of the date of the last dose of study treatment in the double-blind treatment period if the patient did not enter the RW period. A TEAE will only be counted in the RW period if it starts on or after the first dose of study treatment in the RW period and within 30 days of the date of the last dose of study treatment in the RW period.

The number and percent of participants with TEAEs, TEAEs leading to discontinuation from study, Deaths, SAEs and TESAEs will be presented by treatment group for the Treatment Period, and by treatment sequence for the RW Period separately.

The number and percentage of participants reporting TEAEs in each treatment group for the Treatment Period, by treatment sequence for the RW Period, will be tabulated by system organ class (SOC) and preferred term and further categorized by the investigator's assignment of severity. If more than 1 AE is coded to the same preferred term for the same participant, the participant will be counted only once for that preferred term using the greatest severity for the summarization. Additionally, the number and percentage of participants reporting treatment related TEAEs and treatment related TESAEs in each treatment group for the Treatment Period, by treatment sequence for the RW Period, will be tabulated by system organ class (SOC) and preferred term.

In addition, separate tabular displays for participants who died, participants with SAEs, participants with TEAEs leading to discontinuation from study will be presented.

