With respect to laboratory findings, in some participants, glycemic control appeared to be negatively affected by the introduction of relamorelin. There were trends in increasing hemoglobin A1c (HbA1c) values after the initiation of relamorelin, which changed little after approximately 8 weeks, and dose-related trends in fasting hyperglycemia. Otherwise, no clinically relevant abnormalities were seen for other laboratory tests, including liver function tests, electrocardiograms (ECGs), physical examination findings, and injection site reactions; anti-drug antibodies were not found.

A detailed description of the chemistry, pharmacology, efficacy, and safety of relamorelin is provided in the investigator's brochure (Relamorelin Investigator's Brochure).

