9.2.1. Time Period and Frequency for Collecting AE and SAE Information

All AEs and SAEs will be collected from the signing of the Informed Consent Form (ICF) until 30 days after the final visit in the study (Visit 8) or Early Termination Visit, at the time points specified in the SoA ([Section 2](#)). Ongoing AEs at the end of study RLM-MD-01 and RLM-MD-02, and new AEs that occur after the signing of the ICF for RLM-MD-03 are considered to be AEs in RLM-MD-03.

Relamorelin

All SAEs will be recorded and reported to the sponsor or designee within 24 hours, as indicated in [Appendix 4](#). The investigator will submit any updated SAE data to the sponsor within 24 hours of it being available.

Investigators are not obligated to actively seek AE or SAE in former study participants. However, if the investigator learns of any SAE, including a death, at any time after a participant has been discharged from the study, and he/she considers the event to be reasonably related to the study treatment or study participation, the investigator must promptly notify the sponsor.

The method of recording, evaluating, and assessing causality of AEs and SAEs and the procedures for completing and transmitting SAE reports are provided in [Appendix 4](#).

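### The SAP 11.1 table of AEs leading to discontinuation omits withdrawals due to an unworsened AE that began in the lead-in, so it can disagree with disposition

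*SAP*

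**What the plan says.** SAP 11.1 opens with a two-part definition. An AE is treatment-emergent if it was present after the first dose, or if it "was present before the date of the first dose of study intervention and increased in severity or became serious after the first dose". Because "a new AE record will be created with a new AE onset date for any AE that worsens", the SAP reduces this to a date rule: "TEAEs can simply be identified as those AEs with recorded onset date on or after the date of the first dose of study intervention", with an upper limit of 30 days after the last dose. The opening of SAP 11 fixes which first dose is meant: "The Day 1 for the safety analyses in the double-blind treatment period is the date of the first double-blind study treatment in this study". The counting rule for the Treatment Period in SAP 11.1 has the same anchor, since the event must start on or after the first dose in that period.

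The overview counts in SAP 11.1 cover TEAEs, TEAEs leading to discontinuation, deaths, SAEs and treatment-emergent SAEs. The separate displays cover deaths, SAEs and, for withdrawals, "participants with TEAEs leading to discontinuation from study will be presented". SAEs are listed apart from treatment-emergent SAEs, so the SAE and death displays carry no treatment-emergent limit. The withdrawal display does.

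On the other side, SAP 4.1 and protocol 5.1 say that participants continue the blinded treatment they had in the lead-in. Protocol 9.2.1 says which events belong to this study: "Ongoing AEs at the end of study RLM-MD-01 and RLM-MD-02, and new AEs that occur after the signing of the ICF" for RLM-MD-03 are its AEs. SAP 7 summarises discontinuation reasons by treatment group and lists every premature discontinuation from the Treatment Period by reason.

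**The concern.** In most trials, onset on or after the first dose separates events on drug from events before it. Here it does not. First dose in RLM-MD-03 comes after 12 weeks of the same blinded treatment, so an AE that began in the lead-in and is still present began on drug and is an AE of this study under protocol 9.2.1. If it persists unchanged and the participant eventually stops because of it, the onset filter removes the case from the one AE table meant to show AE withdrawals.

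The lead-in cannot report it as a withdrawal, because inclusion criterion 1 requires that the participant completed that study. Under protocol 8 and 8.1, stopping treatment means leaving the study, so no separate table of treatment discontinuations would catch it.

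Two things are at stake. The coded reason (SOC and preferred term) for some on-drug AE withdrawals is lost from the tables, and a reader who compares the AE table with disposition may find different counts with no explanation.

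**Working it through.** The plan states no figure on this point, so the check applies its rules to each kind of AE that starts in the lead-in and leads to withdrawal in RLM-MD-03.

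Inputs:
- TEAE onset rule, new-record rule and list of displays: SAP 11.1.
- First dose means first dose in this study: opening of SAP 11, and the counting rule in SAP 11.1.
- Ongoing lead-in AEs are AEs of this study: protocol 9.2.1.
- Discontinuation reasons by arm: SAP 7.

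| Lead-in-onset AE leading to withdrawal here | Table of TEAEs leading to discontinuation | SAE display | Death display | In any AE table |
|---|---|---|---|---|
| Not worsened, non-serious | No | No | No | **No** |
| Not worsened, already serious | No | Yes | No | Yes |
| Not worsened, fatal | No | Yes | Yes | Yes |
| Worsened here, non-serious | Yes | No | No | Yes |
| Worsened or became serious here, serious | Yes | Yes | No, unless fatal | Yes |

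The Yes entries in the withdrawal column of the last two rows assume that the change produces a new record with a new onset date, and that the withdrawal is attributed to that record. The third row is included for completeness, since an AE that becomes fatal would ordinarily have been re-recorded as worse.

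The first three rows are therefore missing from the withdrawal table, and only the first row is in no AE table. In that row the participant appears in SAP 7 under the reason *Adverse event*, with no SOC or preferred term specified there.

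Size: let W be the AE withdrawals in an arm and f the share whose AE began in the lead-in and did not worsen. The table shows W × (1 − f), so the relative shortfall is f whatever the enrolment. The documents give neither W nor f for this study, by arm or overall.

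The nearest figures are the Phase 2b withdrawals for treatment-emergent AEs in protocol 3.2:
- Relamorelin, 10, 30 and 100 µg BID pooled: 20/289 = 6.9%.
- Placebo: 3/104 = 2.9%.
- Relamorelin 10 µg BID, the only relamorelin dose here: 3 withdrawals, group size not given. Assuming 80 to 110 participants, the rate is 3/110 = 2.7% to 3/80 = 3.8%.

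At the dose under study these figures show no clear excess over placebo, and they say nothing about f.

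**The case against.** The strongest reply is that little is lost. A worsening AE is re-recorded and counted, SAEs and deaths have unrestricted displays, and SAP 7 gives the full count of AE withdrawals by arm whatever the onset. The coded term may be recoverable too, because SAP 15.5 deals with AEs that started before the first dose and mentions data listings. To be missed, an AE must be tolerated through a completed lead-in, get past exclusion criterion 3 (unresolved AEs that the investigator thinks limiting), never worsen, and then cause withdrawal. All of this stands, and it confines the gap to the first three rows of the table above. It does not close it: the withdrawal table still omits those cases, and SAP 11.1 itself specifies no AE listing.

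It can also be said that the definition is coherent. If *present after the first dose* covered ongoing AEs, the second part of the definition would be redundant, so the first part must mean newly present. That is probably the intent. The wording still reads literally the other way, while the date rule is clear, so the two should be aligned.

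Three stronger readings are tempting but unsupported:
- **That the omitted cases are those most likely to be drug-related and fall mainly on relamorelin.** Protocol 3.2 reports an HbA1c trend after starting relamorelin, "which changed little after approximately 8 weeks", which would place it within the lead-in. That is a laboratory trend, not evidence on AE withdrawals, and the Phase 2b count at 10 µg BID does not support it.
- **That a definite number of participants is hidden.** Any such number would need the planned 480 per arm, an assumed withdrawal rate and an assumed f. Early termination (SAP 4 and 13) has overtaken the first, and the documents support neither of the others.
- **That the SAP breaches the protocol.** Protocol 9.2.1 governs collection and attribution. Protocol 10.3.3 leaves safety definitions to the SAP and prescribes no withdrawal table.

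Early termination reduces the number of cases and leaves only an abbreviated report. Safety summaries are nevertheless what that report mainly contains, so the table should be right.

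**Conclusion.** The point holds in a limited form. Under SAP 11.1 as written, a withdrawal due to a lead-in-onset AE that did not worsen is left out of the table of AEs leading to discontinuation. If the AE is also non-serious and non-fatal, no AE table of this study contains it, and it survives only as a reason in disposition. The two counts can then differ without explanation.

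This rests on reading the onset rule as anchored to first dose in RLM-MD-03, which SAP 11 states, and on the SAE display being unrestricted, which follows from SAEs and treatment-emergent SAEs being listed separately. The number of cases and the split by arm are unknown, and the number may be zero. A reader should not infer that all lead-in-onset AE withdrawals disappear, that AE withdrawals go uncounted, or that the omission favours relamorelin.

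**What to change.** In SAP 11.1:
- Tabulate all AEs leading to discontinuation from study by SOC, preferred term and treatment, regardless of onset. This extends to withdrawals what the SAP already does for SAEs and deaths.
- Flag each event as starting in the lead-in (on or after the first lead-in dose) or in this study.
- Reconcile the count with the reason *Adverse event* in the SAP 7 disposition table and explain any difference. Disposition uses the ITT Population and the AE tables use the Safety Population, so participants who were dispensed treatment but not dosed could also cause a mismatch.
- Reword the first part of the TEAE definition so that it says the same as the onset-date rule.

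The cost is SAP wording and one changed table filter. The protocol already treats ongoing lead-in AEs as AEs of this study, so no new data collection is needed. The stated AE withdrawal rate may rise slightly, and the onset flag keeps the TEAE-only count readable beside it.

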11.2 Clinical Laboratory Parameters

Clinical laboratory test values from all assessments (including those from unscheduled or repeat assessments) will be considered potentially clinically significant (PCS) if they meet either the lower-limit or higher-limit PCS criteria listed in [Table 11.2-1](#).

The number and percentage of participants who have PCS postbaseline clinical laboratory values will be tabulated by treatment group for the Treatment Period and by treatment sequence for the RW Period. The percentages will be calculated relative to the number of participants with available non-PCS baseline values and at least 1 postbaseline assessment for periods. The numerator will be the total number of participants with available non-PCS baseline values and at least 1 PCS postbaseline value by treatment group for the Treatment Period and by treatment sequence for the RW Period.

Table 11.2–1. Criteria for Potentially Clinically Significant Laboratory Tests

| Parameter | SI Unit | Lower Limit | Higher Limit |
|----------------------------------|--------------------|--------------------|---------------------|
| CHEMISTRY | | | |
| Albumin | g/L | < 0.9 * LLN | > 1.1 * ULN |
| Alanine Aminotransferase (ALT) | U/L | — | ≥ 3 * ULN |
| Alkaline Phosphatase | U/L | — | ≥ 3 * ULN |
| Aspartate Aminotransferase (AST) | U/L | — | ≥ 3 * ULN |
| Calcium | mmol/L | < 0.9 * LLN | > 1.1 * ULN |
| Chloride | mmol/L | < 0.9 * LLN | > 1.1 * ULN |
| Cholesterol | mmol/L | — | > 1.6 * ULN |
| Creatinine | μmol/L | — | > 1.3 * ULN |
| Potassium | mmol/L | < 0.9 * LLN | > 2.0 * ULN |
| Glucose, Fasting | mmol/L | < 0.9 * LLN | > 2.5 * ULN |
| Glycohemoglobin A1C | % | | Increase of ≥ 0.5% |
| Glycohemoglobin A1C | % | | Increase of ≥ 1% |
| Sodium | mmol/L | < 0.9 * LLN | > 1.1 * ULN |
| Total Bilirubin | μmol/L | — | > 1.5 * ULN |
| Total Protein | g/L | < 0.9 * LLN | > 1.1 * ULN |
| Triglycerides, Fasting | mmol/L | — | ≥ 3 * ULN |
| Urea (BUN) | mmol/L | — | > 1.2 * ULN |
| Magnesium | mmol/L | < 0.9 * LLN | > 1.1 * ULN |
| Bicarbonate | mmol/L | < 0.9 * LLN | > 1.1 * ULN |
| Phosphate | mmol/L | < 0.9 * LLN | > 1.1 * ULN |
| Uric Acid | μmol/L | < 0.9 * LLN | > 1.1 * ULN |
| HEMATOLOGY | | | |
| Basophils Absolute Cell Count | 10 ⁹ /L | — | > 3 * ULN |
| Eosinophils Absolute Cell Count | 10 ⁹ /L | — | > 3 * ULN |
| Hematocrit | Ratio | < 0.9 * LLN | > 1.1 * ULN |
| Hemoglobin | g/L | < 0.9 * LLN | > 1.1 * ULN |
| Lymphocytes Absolute Cell Count | 10 ⁹ /L | < 0.8 * LLN | > 1.5 * ULN |
| MCH | PG | — | > 3 * ULN |
| MCHC | G/L | — | > 3 * ULN |
| MCV | fL | < 0.9 * LLN | > 1.1 * ULN |
| Monocytes Absolute Cell Count | 10 ⁹ /L | — | > 3 * ULN |
| Neutrophils Absolute Cell Count | 10 ⁹ /L | < 0.8 * LLN | > 1.5 * ULN |
| Platelet Count | 10 ⁹ /L | < 0.5 * LLN | > 1.5 * ULN |

Table 11.2–1. Criteria for Potentially Clinically Significant Laboratory Tests

| Parameter | SI Unit | Lower Limit | Higher Limit |
|--|---------------------|--------------------|---------------------|
| Red Blood Cell Count (Erythrocyte Count) | 10 ¹² /L | < 0.9 * LLN | > 1.1 * ULN |
| White Blood Cell Count | 10 ⁹ /L | < 0.7 * LLN | > 1.5 * ULN |
| URINALYSIS | | | |
| pH | | < 0.9 * LLN | > 1.1 * ULN |
| Specific Gravity | | — | > 1.1 * ULN |

LLN: Lower limit of normal value provided by the laboratory.

ULN: Upper limit of normal value provided by the laboratory.

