3.3. Benefit/Risk Assessment

Based on information about relamorelin obtained to date, the benefits of study participation are expected to include accelerated GE and clinically meaningful improvement in the symptoms of DG, including nausea, abdominal pain, postprandial fullness, bloating, vomiting frequency, early satiety, and vomiting severity. A potential risk of treatment is worsening of glycemic control, including the possibility of diabetic ketoacidosis occurring. However, preventive measures, including special laboratory assessments to allow early recognition by investigators and participants of rising glucose levels, are being included in this protocol so that early remedial action (eg, adjustment of medication and diet) may be taken to minimize increase in glucose levels; this might increase the incidence of hypoglycemic reactions, especially in participants with T1DM. See Section 5 Study Design for details of study procedures, dose, and study design justification.

More detailed information about the known and expected benefits and risks and reasonably expected AEs associated with relamorelin are provided in the investigator's brochure (Relamorelin Investigator's Brochure); information about the investigational directions for use for the pen injector, the device that will be used to administer study treatment are also provided.

Relamorelin

4. Objectives and Endpoints

Objectives	Endpoints

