10.3.3. Safety Analyses

All safety analyses will be performed on the Safety Population.

The following safety categories will be summarized as appropriate (eg, categorical or continuous descriptives, shift tables) for the safety population and will be fully defined in the SAP.

- AEs
 - Clinically significant hyperglycemia- and hypoglycemia-related events
- Clinical laboratory assessments
 - Potential Hy's law cases
- Vital signs
- ECGs
- Study-specific assessments
 - HbA1c

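### SAP 11.2 defines PCS laboratory values without direction, so a participant who is high at baseline cannot count as a new low (or the reverse), and new lows and new highs are not told apart

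*SAP*

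**What the plan says.** SAP 11.2 sets up the laboratory summary in three steps.

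- **Status.** Values from all assessments "will be considered potentially clinically significant (PCS) if they meet either the lower-limit or higher-limit PCS criteria" in Table 11.2-1. The status carries no direction.
- **Denominator.** "The percentages will be calculated relative to the number of participants with available non-PCS baseline values and at least 1 postbaseline assessment for periods".
- **Numerator.** The "total number of participants with available non-PCS baseline values and at least 1 PCS postbaseline value".

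The results "will be tabulated by treatment group for the Treatment Period and by treatment sequence for the RW Period". No other axis is named. Fasting glucose is one of the rows with two limits: "Glucose, Fasting | mmol/L | < 0.9 * LLN | > 2.5 * ULN".

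SAP 15.3 adds that every postbaseline assessment is used for PCS determination and that all assessments are listed. No section makes the baseline filter or the postbaseline count specific to low or high.

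On the clinical side, Protocol 3.3 names worsening glycemic control as a potential risk. Of the early remedial action meant to limit it, the same section says that "this might increase the incidence of hypoglycemic reactions, especially in participants with T1DM". Protocol 10.3.3 lists "Clinically significant hyperglycemia- and hypoglycemia-related events" among the adverse event summaries, and Protocol 12.4.1 makes inadequate diabetes control, in both directions, an adverse event of special interest.

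**The concern.** An incidence of new abnormalities normally asks, for each direction, who was free of that abnormality at baseline and then developed it. SAP 11.2 asks instead who was free of any abnormality and then developed any. For a two-sided parameter this has two consequences.

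1. A participant abnormal in one direction at baseline leaves the count for the opposite direction too, although still at risk of it.
2. A fall below the low limit and a rise above the high limit are counted as the same event.

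For fasting glucose both directions are safety topics. Participants who start high are plausibly those whose diabetes treatment is adjusted, and so those in whom new lows are of interest. That link is an inference from Protocol 3.3, not a statement in it. At stake is whether the one planned laboratory incidence table can answer the question that Protocol 3.3 raises.

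**Working it through.** The plan states no figure for this point, so there is nothing to reproduce. The check is a row count and an enumeration of the rule.

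**Rows affected (Table 11.2-1).**

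| Block | Both limits | Upper only | HbA1c increase | Total |
|---|---|---|---|---|
| Chemistry | 11 | 8 | 2 | 21 |
| Hematology | 8 | 5 | 0 | 13 |
| Urinalysis | 1 | 1 | 0 | 2 |
| All | 20 | 14 | 2 | 36 |

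The point concerns the 20 two-sided rows, among them fasting glucose, potassium, sodium, calcium and white cell count.

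**Rule applied to each baseline and postbaseline pattern.** Entries are in denominator / in numerator (1 = yes, 0 = no).

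| Baseline | Postbaseline | SAP 11.2 | New low, own direction | New high, own direction |
|---|---|---|---|---|
| Normal | Low | 1 / 1 | 1 / 1 | 1 / 0 |
| Normal | High | 1 / 1 | 1 / 0 | 1 / 1 |
| High | Low | 0 / 0 | 1 / 1 | 0 / 0 |
| Low | High | 0 / 0 | 0 / 0 | 1 / 1 |

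The first two rows are identical under SAP 11.2, so direction is lost. The last two vanish from it, although each is a new abnormality in its own direction.

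**Split output rows.** Suppose the programmed table prints a low row and a high row. If the baseline filter keeps the undirected status, the high-to-low participant is still removed from the low row. Splitting rows alone cures the pooling but not the exclusion.

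**Size of the exclusion.** Let N be the arm size, h the share PCS-high at baseline, and r the share of those who later go PCS-low. Participants wrongly left out of the new-low denominator = N × h. New lows left uncounted = N × h × r. The documents give neither h nor r. Purely as an assumption, with the planned N = 480 and h from 5% to 30%:

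- 480 × 0.05 = 24 participants per arm
- 480 × 0.30 = 144 participants per arm

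These are participants excluded, not events lost, and the planned arm size need not apply to a study that stopped early.

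**What a pooled row can show.** Take H and L as the new-high and new-low rates and, for illustration only, treat them as independent: pooled = 1 − (1 − H)(1 − L). Assume both rise on relamorelin.

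- Highs 18% v 10%, lows 10% v 4%: 1 − 0.82 × 0.90 = 26.2% v 1 − 0.90 × 0.96 = 13.6%.
- Highs 10% v 4%, lows 18% v 10%: 1 − 0.90 × 0.82 = 26.2% v 1 − 0.96 × 0.90 = 13.6%.

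The overall excess is visible and the same in both cases, but the row cannot say which direction carries more of it.

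**The case against.** The strongest reply is that the either-limit sentence classifies a single value and does not prescribe a table layout. Table 11.2-1 keeps separate lower and higher columns and gives HbA1c two nested increase criteria. The stricter of these would add nothing under one status per parameter, which suggests tabulation by criterion. If output is by criterion, the baseline filter might be read by criterion too. This stands in part: one pooled row is the literal reading, not a certainty. The baseline filter is firmer, because it uses the status exactly as SAP 11.2 defines it and nothing narrows it.

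It can also be said that nothing is lost. SAP 15.3 lists every assessment. Protocol 9.2.7.2 has clinically significant glucose events in either direction reported as adverse events, and SAP 11.1 tabulates treatment-emergent events by preferred term with no laboratory-baseline exclusion. That is right and limits the weight of the point. It does not replace the laboratory incidence: the SAP plans no shift table and no change-from-baseline laboratory summary that would restore direction.

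Two stronger readings should be resisted. A reader might infer that a rise in highs could be cancelled by a fall in lows, hiding harm. That needs lows to fall on relamorelin, whereas Protocol 3.3 anticipates more hypoglycemia; if both rise, the pooled row still shows the overall excess. A reader might also infer that a sizeable share of hypoglycemia goes uncounted. The excluded share is not the event share, and the documents support no figure for either.

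**Conclusion.** The point holds, and it is modest. As written, SAP 11.2 applies an undirected PCS status to the baseline exclusion and to the postbaseline count. For the 20 two-sided rows, high-to-low and low-to-high changes cannot be counted, and new lows and new highs are not distinguished. This follows from the text alone and does not depend on which visit supplies the laboratory baseline.

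Its numerical effect cannot be sized from the documents, and the 24 to 144 participants per arm above rest wholly on assumed baseline shares and the planned arm size. The effect is confined to one descriptive table on which no test depends, in an abbreviated report. It is a cheap improvement, worth making chiefly for fasting glucose.

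**What to change.** Replace the counting rule in SAP 11.2 with wording such as:

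> For parameters with both limits, PCS-low and PCS-high are tabulated separately. For each direction the denominator is participants with an available baseline value that is not PCS in that direction and at least 1 postbaseline assessment in the period; the numerator is those of them with at least 1 postbaseline value PCS in that direction. For the HbA1c increase criteria the denominator is participants with an available baseline and at least 1 postbaseline value.

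The HbA1c sentence is needed because those two criteria are defined by change from baseline, so a baseline value cannot itself meet or fail them. Requiring an available baseline keeps participants with missing baselines out of the denominator, as SAP 11.2 already does.

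The cost is a short SAP edit and a slightly longer table. No new data are needed, and no PCS limit changes.
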